This section specifically refers to data collected about potential subjects who are screened, but have not signed consent, for example potential subjects whose medical record is reviewed to see if they are potentially eligible, potential subjects who respond to a telephone screening call where the research team records information about the potential subject, etc. In this section "Screening Data / Screening Log" refers to any form of data collection on potential subjects who have not yet signed consent. For more information, refer to https://privacyruleandresearch.nih.gov/clin_research.asp.

Will a screening data collection form/screening log be used in this research study?

Yes No

If Yes, respond to all of the following:

1. *Check to confirm you have submitted the Screening Data Collection Form / Screening Log to the IRB.*
2. *Review the following and provide information about the Screening Data / Screening Log and how it will be used (check all that apply):*
 - a. *De-identified Screening Log will be provided to and/or viewed by the Study Sponsor (the log does not record any [HIPAA identifiers](#) or contain protected health information (PHI)).*
 - i. *Explain how the Screening Log will be "distributed to" or viewed by the study Sponsor, i.e., how the Screening Log be e-mailed, sent to and /or viewed by the study Sponsor:*
 - b. *Identifiable Screening Log that will **not** be distributed or viewed outside of the institution (although the Screening Log will record [HIPAA identifiers](#), the Screening Log will **not** leave the institution.)*
 - i. *Specify the identifiers that will be collected (e.g. date of admission or clinic visit, medical record #, and reason the person was not eligible for the study):*
 - c. *Identifiable Screening Log that will be distributed or viewed outside of the institution.*

Consider whether these identifiers could be removed from the Screening Log. It might be possible to eliminate HIPAA identifiers or use a screened subject identifier code and maintain a separate key to the code so no PHI will leave the institution.

If it is necessary to include HIPAA identifiers in the screening log, address the following:

- i. *The rationale for including HIPAA identifiers in the Screening Log:*
- ii. *A plan for protecting the privacy and confidentiality of screened subjects. Screened subjects might or might not be enrolled in the research study, and since screened subjects will not have consented to the use of their PHI for research purposes, it is especially important to protect their privacy and confidentiality. The plan should include keeping identifiers to a minimum, and keeping the Screening Log in a secure location (password protected computer location only accessible by the research team or a locked file cabinet in a locked office, only accessible by the research team):*

Note: A Screening Data Collection Form / Screening Log that contains identifiers and/or PHI must NOT be sent to the study Sponsor UNLESS the IRB has granted a waiver of consent/authorization for this component of the study (or unless the investigator has obtained IRB approved consent and research authorization from each study subject whose name is on the log.)

G.5 Provisions to Protect the Privacy Interests of Subjects

1. *Describe the steps that will be taken to protect subjects' privacy interests (e.g. ensuring that discussion of the study will take place in a private area where subjects cannot be overheard):*
Initial discussion of the study and informed consent will be held in a private area of the pre-op unit, either at the patients' bedside or in a private room, depending on individual circumstances.
2. *Describe the steps that will be taken to make the subjects feel at ease with the research situation in terms of the questions being asked and the procedures being performed. "At ease" does not refer to physical discomfort, but the sense of intrusiveness a subject might or might not experience in response to questions, examinations, and procedures (e.g. ensuring that subjects are comfortable with the research team members performing the study procedures):*
The research subjects will be assured that their interaction with any member of the research team, as well as the information they share, is optional and confidential.

G.6 Provisions to Monitor the Study to Ensure the Safety of Subjects

1. *Describe the plan to periodically evaluate the data regarding both harms and benefits to assess subject safety as follows:*
 - a. *The data that will be reviewed, including safety data, untoward events, and efficacy data:*
Safety information and adverse events that will be collected includes patient agitation and ear injury/hearing issues.
 - b. *Who will review the data:*
For the purposes of this study, the principal investigator will periodically evaluate the safety data and assess the risks and benefits to assess subject safety.
 - c. *How the safety information will be obtained and documented (e.g., case report forms, by telephone calls with participants, printouts of laboratory results, etc.):*
The standard of care at Tufts Medical Center is to collect safety information on all patients undergoing surgery through an established computerized system called Anesthesia Touch. This study will also utilize this system to monitor research safety information.
 - d. *The frequency of data collection, including when safety data collection starts:*
Information will be obtained after subject consent with frequency of data collection aligning with the standard of care at Tufts Medical Center.
 - e. *The frequency or periodicity of review of cumulative data:*
Standard safety data review intervals per Tufts Medical Center protocols.
 - f. *The statistical tests for analyzing the safety data to determine whether harm is occurring:*
The statistical tests that will be performed on the safety data to determine whether harm is occurring will include a chi-squared test, to compare proportions between groups.
 - g. *Any conditions that trigger an immediate suspension of the research or other action for the research:*
In the unlikely event of serious patient harm or an unreasonable level of interference with the standard of care at Tufts Medical Center.

2. *Describe the entity responsible for monitoring the data, and their respective roles (e.g., the investigators, the research sponsor, a coordinating or statistical center, an independent medical monitor, a Data and Safety Monitoring Board (DSMB) /Data Monitoring Committee (DMC), and/or some other entity, and the timeframe for reporting events to this entity:*
As mentioned above, the principal investigator will periodically evaluate the safety data and assess the risks and benefits to assess subject safety.
3. *A copy of the DSMB/DMC Charter if the study is enclosed with the submission:* Yes N/A

G.7 Subject Populations & Vulnerable Populations

1. Can or will pregnant women be enrolled?

Yes No

If Yes, respond to all of the following:

- a. *Describe any preclinical studies, including studies on pregnant animals, and clinical studies, including studies on non-pregnant women, that have been conducted that provide data for assessing potential risks to pregnant women and fetuses:*
There are no additional known potential risks to pregnant individuals or their fetuses other than those described in section B.2.
- b. *Are there any risk to the fetus from the study interventions or procedures? If yes, describe:* or
 No, there are no risks to the fetus from the study interventions or procedures.
- c. *Do the study interventions or procedures hold out the prospect of direct benefit for the woman or the fetus? If yes, describe:*
Potential benefits for the pregnant individual are as described in section B.3. Benefits to the fetus are unknown, though may occur indirectly from benefits to the pregnant individual.
- d. *If there is no prospect of benefit to the fetus, clarify whether the risk to the fetus is NOT greater than Minimal Risk, and whether the purpose of the research is the development of important biomedical knowledge which cannot be obtained by any other means:* N/A
- e. *The biomedical knowledge that is expected to result from this research for this population:*
Potential anxiety-reducing effects of listening to music before non-emergent cesarean section.
- f. *How any risk of this research is the least possible for achieving the objectives of the research:*
No increased risk over the standard of care.
- g. *How mothers providing consent are informed of the reasonably foreseeable impact of the research on the fetus or neonate:*
Standardized verbiage that is consistent with the general consenting process for all potential participants.
- h. *Check to confirm that no inducements, monetary or otherwise, will be offered to terminate a pregnancy and that in the case of a fetus, the fetus is not the subject of a planned abortion.*
- i. *Check to confirm that individuals engaged in the research will have no part in any decisions as to the timing, method, or procedures used to terminate a pregnancy or in determining the viability of a neonate.*

2. Can or will the research involve neonates of uncertain viability or non-viable neonates?

Yes No

3. Can or will subjects who are not yet adults (neonates, children, teenagers) be enrolled?

Yes No

4. Can or will minors who are:

- i) married, widowed, divorced; or
- ii) the parent of a child; or
- iii) a member of any of the armed forces; or
- iv) pregnant or believes herself to be pregnant; or
- v) living separate and apart from his/her parent or legal guardian, and is managing his/her own financial affairs

be approached for study participation for either themselves or their child?

Yes No

5. Can or will wards of the state and/or children at risk of becoming wards of the state be enrolled (this includes foster children or any child that is in state custody)?
 Yes No
6. Can or will cognitively impaired adults (adults with impaired-decision making capacity) or adults who may lose the capacity to consent be enrolled?
 Yes No
7. Can or will prisoners be enrolled?
 Yes No
8. Can or will students and/or employees be **targeted** for enrollment in this research?
 Yes No
9. Transgender Subjects: Are you recording sex or gender for your study?
 Yes No

H. Adverse Event Monitoring

H.1 Definitions

Define adverse events (AEs), serious adverse events (SAEs), and unanticipated problems for your study:

N/A, no physical risks are anticipated with this research study, and we will use the definitions in the Tufts Health Sciences IRB's [Reportable New Information policy](#).

H.2 Reporting Procedures

1. *Describe the protocol-specific reporting procedures, including who will be responsible for each step (e.g., PI, Data Coordinating Center, Medical Monitor), which forms should be completed, timeframes for reporting, how reports will be distributed, and what follow-up is required:*

Patients are routinely monitored for development of adverse events as part of their anesthetic care. This occurs on a continuous basis from the moment the anesthetic is administered until the moment the patient is discharged home. Monitoring of patients during the study intervention prior to anesthetic care will be done by the co-investigator, [name], who will coordinate with clinical staff to ensure patient safety. Specifically, the co-investigator will monitor for participant ear injury or agitation. A computerized system exists which alerts clinicians to the development of some adverse effects, which are recorded in the medical record. The co-investigator, will be alerted in these situations and all adverse events will be forwarded to the principal investigator. Clinicians are alerted to events immediately as they occur. Clinical staff are trained to deal with such events. The co-investigator, will be responsible for contacting the principal investigator to report the occurrence of adverse events. The principal investigator will then complete any necessary safety forms, including the Anesthesia Department's Quality Assurance form. The events will be reported within 24 hours to the QI director and the chairman of the department.

H.3 Reportable New Information

Check to confirm that reportable new information will be reported to the IRB per the Tufts Health Sciences IRB's [Reportable New Information policy](#). If your reporting plan to the IRB differs from the IRB's policies, please describe it in detail or specify where this information is in the protocol:

I. Statistical Considerations

I.1 Study Endpoints

1. *Describe the primary and secondary study endpoints:*

Primary endpoint: determination of the 95th percentile effective dose of music duration for anxiety reduction.

Secondary endpoint: compare the 95th percentile effective dose of music duration for anxiety reduction between the Mozart and personal-preference intervention arms.

Secondary endpoint: analyze and compare pre-and post-intervention heart rate and blood pressure measurements.

Exploratory endpoint: analyze and compare anxiety ratings at the three post-intervention event-point measurements.

Exploratory endpoint: analyze and compare anxiety ratings using the 0-10 scale with the STAI questionnaire.

2. *Describe any primary or secondary safety endpoints:* N/A

I.2 Sample Size Justification Statistical Analyses

1. *Describe the statistical analyses that will be performed for this study:*

Statistical analysis to determine the ED₉₅ will be conducted using the methods described by Pace, Stylianou, and Warltier (8).

2. *Provide a sample size justification:*

The plan is to enroll up to 33 subjects per treatment group (up to 66 total), with a minimum goal of 30 per group (60 total). This is based on prior studies that suggest 20-40 study subjects are required for adequate statistical power in sequential allocation biased coin design studies, and we expect a ~10% attrition rate. A goal of 33 subjects per group will thus likely turn into an estimated sample size of 30 after attrition, which falls well within the acceptable sample size range.

I.3 Number of Subjects

1. *Specify the number of subjects to be enrolled in total across all sites:* N/A this is not a multicenter study.

2. *Specify the number of subjects to be enrolled at the Tufts site(s)¹. Subjects who sign an ICF are considered “enrolled”. For studies that have a separate screening ICF, this number is the number of subjects who sign a screening ICF:*

- a. *Specify the number of subjects expected to be enrolled at the Tufts site (i.e. sign the screening or study ICF):*

Up to 66 subjects.

- b. *Estimate the number of subjects needed to complete the study at the Tufts site:* 60 subjects

- c. *Provide the rationale for enrolling this number of subjects at the Tufts site:*

As mentioned above, previous sequential allocation biased coin design studies suggest that 20-40 subjects are required for adequate statistical power.

- d. *If a large number of withdrawals and/or dropouts is expected, explain why:*

Withdrawal/dropout rate is expected to be roughly 10%.

I.4 Data Management

1. *Describe the data analysis plan, including descriptions of the data:*

Data collection forms and an excel spreadsheet with all the analyzed data will be stored during the study period in the PI's private locked office and/or cloud account, where access is exclusive to the research team.

2. *Describe the steps that will be taken to secure the data (e.g., training, authorization of access, password protection, encryption, physical controls, certificates of confidentiality, and separation of identifiers and data) during storage, use, and transmission:*

As mentioned above, physical data will remain in a locked private office to which access is restricted to research team members only. To separate and distinguish ICFs between this study and the previous, similar study (IRB STUDY #00001496), the physical forms will be kept in a folder/binder of a different color with clear labels. All electronic data will be held in a password protected, encrypted account within Tufts CTSI REDCap. Data will be coded. Each participant will be assigned a unique randomly generated three-digit number that will be linked with their medical record number on the key. Duplicates will be

¹ ¹ If Tufts IRB is requested to be the Single IRB of Record for external sites (as per section **Error! Reference source not found.**), include all sites in these enrollment numbers.

prevented via software functions in the original generation of three-digit numbers. No part of the patient's information or MRN will be used to generate the randomly generated number. Once this unique, randomly generated 3-digit number has been assigned, all coded information will utilize this unique identification number. The 3-digit number will replace the patient's MRN on coded data. The only place where the patient's MRN and their unique 3-digit identification number will coexist is on the physical key that will be kept in the PI's locked office as detailed in section G.3.1. Coded data will be stored with a Tufts CTSI REDCap account. Records will be stored for 7 years after the study is closed with the IRB, per IRB policy. The key will be immediately destroyed once the required number of participants have been recruited and the data compiled.

3. *Describe any procedures that will be used for quality control of collected data:* continual collaboration between PI and Co-I on data collection and handling.

I.5 Randomization

Will subjects be randomized?

Yes No

If Yes respond to all of the following:

1. *Describe the randomization procedures, including the ratio of subjects randomized to each study arm:*
Randomization will be performed to assign study subjects to one of the two intervention groups using “randomizer.org” or a similar online program. This will also assign subjects to a random number to help blind later analysis. Ratio of subjects should be 50/50 in each study arm. Determination of music dosage (the duration of music played for participant listening) will be done using the biased coin up-down sequential allocation algorithm, which is not random.
2. *Describe the blinding procedures:* The PI or Co-I administering the study intervention will be unable to remain blind to the study intervention given the inherent nature of the protocol. This will also be true of the participants, as the intervention treatment arms will likely be easily distinguishable. However, the participants will remain blind to their randomized intervention group until the intervention begins. Given the nature of clinical workflow surrounding cesarean sections, blinding of anxiety level assessment will also not be feasible.

J. Drugs or Devices

1. Will the research involve drugs?

Yes No

2. Will the research involve devices?

Yes No

K. Study Administration

K.1 Setting

1. *Describe the sites / locations where your research team will conduct the research, including recruitment activities:*
 - a. *Tufts MC / Tufts University locations (specify which facility/clinic if applicable):*
Tufts Medical Center, Labor and Delivery Unit

K.2 Registration

1. *Describe the steps the research team will take to ensure that a subject is appropriately enrolled or registered in the study prior to receiving any study intervention (e.g. describe and submit any protocol eligibility checklist that will be used, specify who on the research team will confirm eligibility and that consent was documented, etc.):*
The Co-I will ensure subject eligibility, perform the informed consent process, and subsequently perform the study protocol. Eligibility criteria will be consistent with those outlined above in Section D. Thus, there will be no risk of miscommunication between the informed consent process and the study interventions.

K.3 Resources Available

1. *Describe the roles/tasks of each research team member here (or alternatively, you may submit any current Delegation of Authority Log you may have which already has this information completed):*
The research team is composed of the following members:
 - Principal investigator: [name] Assistant professor of Anesthesiology. Primary investigator responsible for the preparation, design, conduct, and administration of the study.
 - Co-investigator: [name], MS4 and Tufts CTS Research Fellow. Responsible for writing the study's protocol under the PI guidance, obtaining the informed consent, managing data collection, and coding and coordinating various sectors in the study.
 - Tufts Medical Center facilities will provide medical resources that might be needed by study subjects.
2. *Describe the qualifications (e.g., training, experience) of the PI and research team to perform their roles. Provide enough information for the IRB to determine the PI and research team are qualified to conduct the proposed research. Alternatively, you can submit the current CVs for the research team instead:*
 - Please see attached CVs
3. *Describe the coverage plan to address any issues (including subject safety issues) that occur while the PI is away and/or unavailable. The research team member designated to serve as the acting PI in the PI's absence should have similar training and expertise as the PI:*
In the absence of the PI, the Co-I will perform duties as able but may temporarily halt research activity until the PI's return if necessary. This is due to the fact that the Co-I has some similar training to that of the PI but not to the same extent (less overall research and clinical experience). If patient safety issues arise while the PI is absent, the Co-I would temporarily halt research activity until the PI's return.
4. *Describe the process to ensure the research team members have adequate oversight and are adequately trained regarding the protocol, study procedures, and their roles and responsibilities:*
There will only be two research team members, the PI and the Co-I, both of whom will be heavily involved and educated on the study protocol, procedures, and their respective roles and responsibilities.
5. *Medical or psychological resources that subjects might need, such as for emergencies or medical issues, are available for the study:* Yes N/A

K.4 IRB Review

1. *Check to confirm that an appropriate IRB, registered with the OHRP, will review and approve this study.*
2. *Check to confirm that any amendments to the protocol or informed consent documents will be reviewed and approved by the IRB prior to use, unless required to eliminate an apparent immediate hazard to subjects.*

K.5 Multi-Site Research

Is this a multi-site study where Tufts IRB is requested to be the Single IRB of record for non-Tufts sites or collaborators, AND/OR where Tufts is the sponsor, primary grant recipient, or coordinating site?:

Yes No

K.6 Community-Based Participatory Research

Can or will this study involve community-based participatory research?

Yes No

K.7 Sharing Results with Subjects

Will results (overall study results or individual subject results, such as results of investigational diagnostic tests, genetic tests, or incidental findings) be shared with subjects or others (e.g., the subject's primary care physician or the subject's treating physician)?

Yes No

L. Nursing Involvement

Will your study require the involvement of Nursing

Yes No

If Yes, respond to all of the following:

1. Describe the research procedures Nursing will do for this study above and beyond their usual nursing practice:
Nursing may assist in acquiring vitals for this study if it coincides with their usual nursing practices.
Nursing is otherwise only asked to help coordinate clinical care with the research procedures that will be carried out by investigators.

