 N/A, there is no direct benefit. However, subjects may experience decreased levels of anxiety as a result of listening to music.
2. *Describe any benefit to the population from which the subject is drawn:*
If proven effective, music could be offered to more patients in the pre-operative setting to help reduce their levels of anxiety and could provide more accurate “dosing” estimates of music duration for clinicians to use.
3. *Describe any benefit to science, society, and humanity in general:*
The results of this study will help further reveal the effect characteristics of music on anxiety.

B.4 Alternatives

1. *Describe alternatives to participating in this research study (e.g. to decide not participate in the study, alternative treatments, no treatment (palliative care), etc.):*
The alternative is not participating in the study.
2. *Describe the standard clinical care that may be an alternative:* N/A
3. *Describe how the subject can receive the research procedures/drug/device used in this study in a non-research setting:* The subject may use their own music-playing devices if so desired

C. Objectives

1. *Describe the purpose, specific aims, or objectives of the study (i.e. the reason for performing the study in terms of the scientific question to be answered):*
The primary objective of this study is to determine effective dose of music duration for anxiety reduction in parturients awaiting non-emergent cesarean section.

A secondary objective of this study is to compare the effective dose of music duration for anxiety reduction between classical pieces previously studied vs. patient-preferred music selection.

An additional secondary objective is to analyze the physiologic impact from anxiety reduction pre- and post-study intervention.

An exploratory objective of this study is to investigate the dose-duration relationship of music on anxiety reduction in patients awaiting non-emergent cesarean section.

D. Enrollment and Withdrawal

D.1 Inclusion Criteria

1. *Describe the criteria that define who will be included in the study as a numbered list:*
 1. Age: 18 years old or older.
 2. Planning a scheduled or urgent (non-emergent, i.e. for arrest of labor) cesarean section.
 3. Able to provide informed consent.
 4. American Society of Anesthesiologists (ASA) physical status rating of II-III. (Mild systemic disease; severe systemic disease that is not incapacitating)

D.2 Exclusion Criteria

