- Once consent is given, the study subjects will be asked to assess their anxiety level on a scale of 0-10, 0 being no anxiety at all. Additionally, they will be asked to complete 6 STAI questionnaire prompts to further assess their anxiety levels. If the score is 0, they will automatically be removed from the study (as per the exclusion criteria). If the score is greater than 0, a baseline heart rate and blood pressure will be recorded, and the participant will proceed to the study intervention.
- All study participants will be also initially asked to choose four songs of personal preference that they would enjoy listening to. These song choices will be written down on their pre-intervention screening questionnaire and later used if their pre-determined music selection falls into the “personal preference” study arm.
- If there are multiple support people present in the room, the participant will be asked to identify a maximum of one person to stay in the room for the study intervention.
- The study intervention includes listening to pre-selected music, randomized to selections either from Conrad, et al. or from their own preference list, for a pre-determined duration ranging from 1-30 minutes. This intervention is being performed exclusively for research purposes and is not part of the standard of care. The study subjects will listen to this music played from a speaker connected to an audio device, both supplied by the research team. The investigator and patient will collaborate on patient positioning (supine, semi-recumbent, seated upright, etc.) to optimize patient comfort during the study intervention. Active participation on the study subjects’ part will be required to continually assess the volume of the music being played to avoid potential tympanic-membrane injury.

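### The only pre-music anxiety rating is taken at consent and both arms receive music, so any change before the music starts is counted as response in the primary ED95, in an unknown direction

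*Combined protocol and SAP*

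**What the plan says.** The primary endpoint in I.1 is "determination of the 95th percentile effective dose of music duration for anxiety reduction", serving the objective in section C to "determine effective dose of music duration for anxiety reduction in parturients awaiting non-emergent cesarean section".

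F.2 Procedures gives the steps as a list:

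- **Baseline.** "Once consent is given, the study subjects will be asked to assess their anxiety level on a scale of 0-10". The six STAI prompts belong to the same step. A score of 0 leads to removal; otherwise heart rate and blood pressure are recorded.
- **Songs.** Four preferred songs are chosen.
- **Room.** If several support people are present, "the participant will be asked to identify a maximum of one person to stay in the room for the study intervention".
- **Music.** Selections are randomized between the Mozart pieces and the participant's own list, "or from their own preference list, for a pre-determined duration ranging from 1-30 minutes". Within this step, "The investigator and patient will collaborate on patient positioning (supine, semi-recumbent, seated upright, etc.) to optimize patient comfort during the study intervention".
- **Afterwards.** Anxiety is rated at three points: at the end of the music, before transport to the OR, and on arrival there.

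No 0-10 rating between the consent-time baseline and the music is described, and no limit is set on that interval. Neither arm is without music, and the range has no zero-minute level. B.1 item 5 describes a control equivalent to standard practice, but no such arm appears in the procedures, the randomization (I.5) or the sample size (I.2). I.5 says durations are set by a biased-coin up-down algorithm and that anxiety assessment cannot be blinded. D.3 says data from withdrawn participants are destroyed.

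**The concern.** The ED95 is meant to be read as a dose of music, and B.1 and B.3 say clinicians could use it as a dosing estimate. The baseline may have been recorded in a different setting from the one in which music starts. Whatever happens to anxiety in between (settling, a quieter room, a more comfortable position, or growing apprehension as surgery approaches) enters the pre-to-post difference and is credited to music.

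The up-down design makes this matter twice. Each outcome helps set the next participant's duration, so background change moves the durations tested as well as the final estimate. With no untreated comparison, nothing in the data can separate the two sources afterwards. Change before the music could, however, be measured at almost no cost, and the plan does not measure it.

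**Working it through.** **1. The plan's own figures.** The documents give no rate of spontaneous change, no repeat-rating SD and no dose-response curve, so there is no stated figure for this point to reproduce. The only related figures are for enrolment (I.2, I.3): 33 × 0.9 = 29.7, about 30 per arm, and 66 − 60 = 6 losses allowed in total. Everything below uses assumed values to show direction and range.

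**2. Background change as a share of participants.** Let F be the share relieved by music at a given duration, p0 the share who would show a fall without music, and r the share of music-relieved participants whose relief is cancelled by rising anxiety. Then

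P(response) = p0(1 − F) + (1 − r)F,

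and the 95% point lies where F = (0.95 − p0)/(1 − r − p0). Take a lognormal curve with music-only ED50 4 min and ED95 15 min (assumed):

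| p0 | r | F needed | Observed ED95 (min) |
|---|---|---|---|
| 0 | 0 | 0.950 | 15.0 |
| 0.2 | 0 | 0.9375 | 13.7 |
| 0.3 | 0 | 0.929 | 13.0 |
| 0.5 | 0 | 0.900 | 11.2 |
| 0.3 | 0.02 | 0.956 | 15.7 |
| 0.3 | 0.04 | 0.985 | 22.8 |

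At r of 0.05 or more, response cannot exceed 1 − r ≤ 0.95 even when F approaches 1, so the 95% point is not reached at any finite duration, whatever p0 is. Across five assumed curves (ED50 4-8 min, ED95 10-28 min), falls alone shorten the ED95 by 6-11% at p0 = 0.2 and by 18-30% at p0 = 0.5.

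**3. The same thing through the design.** A biased-coin sequence was simulated with 30 participants, start at 4 min, 2-minute steps, coin 0.05/0.95 = 0.0526 and an isotonic estimate. The step size and coin are assumed because the plan does not state them. On the same curve the median estimates were:

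| p0 | r | Median estimate (min) |
|---|---|---|
| 0 | 0 | 11.6 |
| 0.3 | 0 | 10.5 |
| 0.5 | 0 | 9.1 |
| 0.3 | 0.1 | 13.4 |
| 0.3 | 0.2 | 17.5 |

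The comparison is with 11.6, the simulated value with no background change.

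**4. Drift and noise in points.** Suppose response means a fall of at least 1 point, so a cut at 0.5 on a continuous scale. Let rating differences have SD s, let m be the mean fall before the music starts, and let music lower anxiety by 1 point per k minutes. A 95% response then needs

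d = k(0.5 + 1.645 s − m).

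With k = 4 min, purely for illustration:

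- No noise, no drift: 4 × 0.5 = 2.0 min.
- s = 1, no drift: 4 × 2.145 = 8.6 min. s = 1.5: 4 × 2.967 = 11.9 min.
- s = 1, settling of 0.5 point before music: 4 × 1.645 = 6.6 min.
- s = 1, rise of 0.5 point before music: 4 × 2.645 = 10.6 min.

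Noise does produce false falls: P(N(0, s) > 0.5) is 0.31 at s = 1 and 0.37 at s = 1.5. It also hides a true 1-point fall with the same probabilities, P(N(1, s) < 0.5). At a 95% target the hidden falls dominate and d rises with s. Letting k vary between participants (lognormal, median 2, 4 or 8 min per point, log-SD 0.3, 0.5 or 0.8) gave a longer ED95 with noise in every case tried. For example, at median 4 and s = 1 it rose from 3.3 to 9.6 min at log-SD 0.3.

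**The case against.** The strongest objection is that no direction can be claimed. A reader might infer from the consent-time baseline that the ED95 is understated. The documents do not support that. B.1 itself says that waiting for the operation can provoke considerable anxiety, so drift may be upward, and symmetric rating noise lengthens the ED95 in the models above. This objection stands in full.

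A reader might also turn the preliminary result in B.1 into a rate, so that each half point of settling is worth 2 minutes. B.1 says only that as few as 4 minutes sufficed for a 1-point reduction; that is not a slope. The 2-minute differences in step 4 follow from the assumed k and from nothing in the plan.

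The sequence is partly inferred. F.2 does not state that its list is chronological, its song-choice item is described as an initial request, and the room step applies only when several support people are present. Consent already takes place in a private setting. What stands regardless is that the rating is tied to consent, positioning sits within the intervention step, and no later pre-music rating is described.

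Response is not defined for this study, nor is it said which of the three later ratings decides it, so a 1-point fall is an assumption here.

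Finally, the secondary comparison, to "compare the 95th percentile effective dose of music duration for anxiety reduction between the Mozart and personal-preference intervention arms", is less affected, because the randomized arms share the same background.

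**Conclusion.** The point holds as a gap in attribution. As written, the primary ED95 combines music with any change between the consent-time rating and the start of music, and the dose path carries the same mixture. Neither direction nor size can be settled from the documents. On the one assumed curve, background falls in up to half of participants and cancelled relief in up to 4% of music responders move a 15-minute ED95 to between 11.2 and 22.8 minutes. Cancellation at 5% or more leaves no attainable 95% point. These figures rest on assumed lognormal curves and background rates and cover all background change, including change during listening, so the part arising before the music is smaller or unknown. The finding that noise lengthens the ED95 assumes a smooth spread of sensitivity across participants.

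A change to the plan is warranted because the remedy is cheap and works whichever way the drift goes. It is only a partial remedy: rating noise, change during listening and the link between longer music and longer elapsed time all remain.

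**What to change.** 1. **F.2:** repeat the 0-10 rating immediately before the music starts, with the room settled and the patient positioned. Use it as the baseline for response and for the score-0 check.
2. **D.3:** amend the destruction rule so that both coded ratings are kept for participants who reach 0 by the second rating. Otherwise the people who settled most would vanish from the report.
3. **Reporting:** give the consent-to-music change for all participants with both ratings, as a description of pre-music drift. It should not be offered as an estimate of change during 1-30 minutes of listening.
4. **C and I.1:** state the primary result as the duration at which 95% report a fall, uncontrolled for elapsed time, rather than as an effect of music alone.

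The cost is one rating of a few seconds, one reported summary and a protocol amendment. The downside is possibly a few more score-0 losses. I.3 counts everyone who signs consent as enrolled, so these come out of the 66 − 60 = 6 losses the plan can absorb. No added arm or larger enrolment target is needed.
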